At least 2 weeks or 5 half-lives (whichever is longer) prior to SCR-2 visit	 Antidepressant drugs Anticonvulsants Antipsychotics (for depot neuroleptics consider long half-lives) Anxiolytics (benzodiazepines, non-benzodiazepines) Hypnotics Centrally acting anticholinergics Mood stabilizers Muscle relaxants (centrally acting with psychotropic effects) Central Alpha-2 Receptor Agonists Sodium oxybate Sedating antihistamines Melatonin and melatonin receptor agonists Stimulants Adenosine Receptor Antagonist Systemic corticosteroids (inhaled corticosteroids are allowed) Diet pills that contain active substance and/or ingredients that can affect sleep Isotretinoin Any recreational drugs, even if used for medicinal reasons Opioids/narcotics Over-the-counter (OTC) /herbal treatments including: Supplements with possible psychotropic effect Extended-release pseudoephedrine Traditional Chinese medicine used for sleep improvement/disturbances 	
PSG = polysomnography, S0	CR = Screening.	

21 SEP 2023 Page: 70 of 73

Table 10-5: Medication with limited use during the study

During the study	Therapies
Allowed up to twice per week	 Non-sedating antihistamines. See Table 10–6 for non- sedating antihistamines which are prohibited during the study as CYP3A4 substrates.
	Pseudoephedrine

CYP3A4 = Cytochrome P450 isoenzyme 3A4.

Table 10-6: Prohibited concomitant medication potentially affecting PK.

Washout period before SCR-2	Therapies
At least 2 weeks or 5 half-lives (whichever is longer) prior to SCR-2 visit: CYP3A4 substrates with a narrow therapeutic range	Alfentanil, astemizole, fentanyl, pimozide, terfenadine
At least 2 weeks or 5 half-lives (whichever is longer) prior to SCR-2 visit: Strong or moderate inhibitors of CYP3A4	Nefazodone, fluvoxamine, tofisopam
At least 2 weeks or 5 half-lives (whichever is longer) prior to SCR-2 visit: Strong or moderate inducers of CYP3A4	Carbamazepine, phenytoin, St. John's wort, phenobarbital, primidone
Washout period before BL	Therapies
From 1 week prior to BL visit: CYP3A4 substrates with a narrow therapeutic range	Cisapride, cyclosporine, dihydroergotamine, ergotamine, quinidine, sirolimus, tacrolimus
From 2 weeks prior to BL visit: Strong or moderate inhibitors of CYP3A4	See Table 10–7 for examples of most common moderate and strong CYP3A4 inhibitors
From 4 weeks prior to BL visit: Strong or moderate inducers of CYP3A4	See Table 10–8 for examples of most common moderate and strong CYP3A4 inducers

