6.3 APPENDIX 3: Identification of Prohibited Medications

Drug groupings, individual drug names and manual review will be used to identify prohibited therapies and medications that were defined in protocol Section 10.7. This includes prior hormonal therapies, medications that affect PK, and medications potentially confounding efficacy that are to be washed out during the screening period as well as the identification of the ICE prohibited concomitant medications impacting efficacy.

The list of prohibited medications together with the pre-defined washout time period for their effect will be reviewed during blind review of the data and finalized prior to unblinding.

Table 6-4: Preliminary list of prohibited hormonal therapies by drug groupings

DGCODEL0	DGNAME0	DGCODEL1	DGNAME1	DGCODEL2	DGNAME2	Impact duration of concomitant medication
		108	Drugs acting on gonadotropin- releasing hormone (GnRH) receptors	109	GnRH agonists	From 1st dose to 12 weeks after the last dose.
		108	Drugs acting on gonadotropin- releasing hormone (GnRH) receptors	110	GnRH antagonists	From 1st dose to 12 weeks after the last dose.
		5	Hormone replacement therapy	2	Oestrogens used in replacement therapy	1, From 1st dose to 4 weeks after the last dose if the route is vaginal, intravaginal, cutaneous, nasal, topical or transdermal. 2, From 1st dose to 8 weeks after the last dose if the route is oral or sublingual. 3, From 1st dose to 12 weeks after the last dose if the route is intramuscular. 4, From 1st dose to 24 weeks after the last dose if the route is sintramuscular. 5, From 1st dose to 24 weeks after the last dose if the route is subcutaneous or intradermal.
		5	Hormone replacement therapy	3	Progestogens used in replacement therapy	1, From 1st dose to 4 weeks after the last dose if the route is vaginal, intravaginal, cutaneous, nasal, topical or transdermal. 2, From 1st dose to 8 weeks after the last dose if the route is oral or sublingual. 3, From 1st dose to 12 weeks after the last dose if the route is subcutaneous or intradermal. 4, From 1st dose to 24 weeks after the last dose if the route is intramuscular.

Version 2.0

DGCODEL0	DGNAME0	DGCODEL1	DGNAME1	DGCODEL2	DGNAME2	Impact duration of concomitant medication
		772	Cancer therapies	738	Endocrine antineoplastic therapy	From 1st dose to 12 weeks after the last dose.

Page: 50 of 57

Table 6-5: Preliminary list of prohibited concomitant medication impacting PK by drug grouping

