DGCODEL0	DGNAME0	DGCODEL1	DGNAME1	DGCODEL2	DGNAME2	Impact duration of concomitant medication
45	Drugs interacting with CYP3A	240	CYP3A inducers	225	Moderate CYP3A inducers	From 1st dose to 4 weeks after the last dose Considered not to have an influence on efficacy, if route is auricular(otic), ophthalmic or conjunctival.
45	Drugs interacting with CYP3A	240	CYP3A inducers	265	Strong CYP3A inducers	From 1st dose to 4 weeks after the last dose

All listed drug names in Table 6-6 were reported in NIRVANA as of finalization of this SAP.

Table 6-6: Preliminary list of prohibited concomitant medication potentially confounding efficacy by drug names

WHO Drug Name	WHO Drug Record Number	WHO Drug Sequence Number 1	Impact duration of concomitant medication
DIPHENHYDRAMINE HYDROCHLORIDE	000004	02	From 1 st dose to 2 weeks after the last dose
BETAMETHASONE DIPROPIONATE;BETAMETHASONE SODIUM PHOSPHATE	000085	13	From 1 st dose to 2 weeks after the last dose if route is oral.
DIAZEPAM	000170	01	From 1 st dose to 4 weeks after the last dose
METHOCARBAMOL	000479	01	From 1 st dose to 2 weeks after the last dose
METHYLPREDNISOLONE	000496	01	From 1 st dose to 2 weeks after the last dose if route is oral
HYDROXYZINE	000584	01	From 1 st dose to 2 weeks after the last dose
HYDROXYZINE HYDROCHLORIDE	000584	02	From 1 st dose to 2 weeks after the last dose

Page: 51 of 57

Version 2.0

WHO Drug Name	WHO Drug Record Number	WHO Drug Sequence Number 1	Impact duration of concomitant medication	
CLONIDINE	001711	01	From 1st dose to 2 weeks after the last dose	
CLONAZEPAM	002852	01	From 1 st dose to 4 weeks after the last dose	
CYCLOBENZAPRINE	004284	01	From 1 st dose to 2 weeks after the last dose	
CITALOPRAM	005826	01	From 1st dose to 2 weeks after the last dose	
CITALOPRAM HYDROBROMIDE	005826	02	From 1 st dose to 2 weeks after the last dose	
TRAMADOL	005992	01	From 1 st dose to 2 weeks after the last dose	
TRAMADOL HYDROCHLORIDE	005992	02	From 1 st dose to 2 weeks after the last dose	
BUPROPION HYDROCHLORIDE	007005	02	From 1 st dose to 2 weeks after the last dose	
TIZANIDINE HYDROCHLORIDE	007407	02	From 1 st dose to 2 weeks after the last dose	
CETIRIZINE HYDROCHLORIDE *	008843	02	From 1 st dose to 2 weeks after the last dose if frequency is once daily (QD) or 3 times per week	
LORATADINE *	009175	01	From 1st dose to 2 weeks after the last dose if frequency is once daily (QD) or 3 times per week	
GABAPENTIN	010030	01	From 1st dose to 2 weeks after the last dose	

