TOPIRAMATE	012017	01	From 1st dose to 2 weeks after the last dose	
VENLAFAXINE HYDROCHLORIDE	012338	02	From 1st dose to 2 weeks after the last dose	
MELATONIN	012432	01	From 1st dose to 2 weeks after the last dose	
FEXOFENADINE HYDROCHLORIDE *	013142	02	From 1st dose to 2 weeks after the last dose if frequency is once daily (QD) or 3 times per week	
FEXOFENADINE;PSEUDOEPHEDRINE HYDROCHLORIDE *	129590	03	From 1st dose to 2 weeks after the last dose if frequency is once daily (QD) or 3 times per week	
DESLORATADINE *	013985	01	From 1 st dose to 2 weeks after the last dose if	

Page: 52 of 57

Version 2.0

WHO Drug Name	WHO Drug Record Number	WHO Drug Sequence Number 1	Impact duration of concomitant medication
			frequency is once daily (QD) or 3 times per week
LEVOCETIRIZINE DIHYDROCHLORIDE *	015302	02	From 1st dose to 2 weeks after the last dose if frequency is once daily (QD) or 3 times per week
BILASTINE *	071040	01	From 1st dose to 2 weeks after the last dose if frequency is once daily (QD) or 3 times per week
ACTAEA RACEMOSA **	014568	01	From 1 st dose to 2 weeks after the last dose
ACTAEA RACEMOSA EXTRACT **	014568	04	From 1 st dose to 2 weeks after the last dose
ACTAEA RACEMOSA EXTRACT;BORON;CALCIUM;FOLIC ACID;GLYCINE MAX EXTRACT;MAGNOLIA OFFICINALIS;NICOTINIC ACID;PYRIDOXINE HYDROCHLORIDE;RIBOFLAVIN;SELENIUM;THIAMI NE;TOCOPHEROL;VITAMIN B12 NOS **	113355	02	From 1st dose to 2 weeks after the last dose
DOXYLAMINE SUCCINATE	003341	02	From 1 st dose to 2 weeks after the last dose
FEZOLINETANT	093415	01	From 1 st dose to 2 weeks after the last dose
HYDROCODONE	000600	01	From 1 st dose to 2 weeks after the last dose
ALPRAZOLAM	005952	01	From 1 st dose to 2 weeks after the last dose
OXYBUTYNIN	005389	01	From 1 st dose to 2 weeks after the last dose
NIRMATRELVIR;RITONAVIR	158921	01	From 1 st dose to 2 weeks after the last dose
TRIAMCINOLONE ACETONIDE	000319	02	From 1 st dose to 2 weeks after the last dose
PHENTERMINE	001317	01	From 1 st dose to 2 weeks after the last dose

^{*} Non-sedating antihistamines/pseudoephedrine are allowed up to twice per week per protocol. Participants with PRN or 'as needed' are considered as taking these medications according to the study protocol.

^{**}These medications belong in the drug grouping DGNAME2 'Oestrogen used in replacement therapy' and should have impact duration specified in this table instead of the impact duration specified in Table 6-4.

Version 2.0 Page: 53 of 57

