6.4.3 Intake of prohibited concomitant medication having impact on efficacy

The list of prohibited concomitant medications that were defined in the protocol to influence efficacy will be finalized prior to unblinding. Missing dates will be imputed as described in Section 4.1.1.4.

PSG assessments during any intake of prohibited medication or intake that occurred prior to the PSG assessment and is within the washout period of the prohibited medication (i.e., within the timeframe specified in the impact duration column of Table 6-4, Table 6-5and Table 6-6) will be considered as an intercurrent event. PSG assessments will be performed on 2 consecutive nights at each visit and if only one of the nights fall within the timeframe, then that night will be discarded while the other night will be included in the analysis. For the identification of this ICE, visit day 30 and day 86 will be used as the PSG assessment day for week 4 and week 12 respectively if PSG assessment(s) are missing. The preliminary list of prohibited concomitant medications are specified in Section 6.3.

Version 2.0 Page: 55 of 57

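### SAP Table 6-6 applies two different route rules to its three corticosteroid entries, and neither matches the protocol's criterion of systemic use with inhaled use allowed

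*SAP*

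**What the plan says.** Protocol 10.7, Table 10-4 lists the class as "Systemic corticosteroids (inhaled corticosteroids are allowed"). Its washout is "At least 2 weeks or 5 half-lives (whichever is longer) prior to SCR-2 visit". The protocol does not define systemic any further.

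SAP 6.3 presents its lists as the implementation of that section: "Drug groupings, individual drug names and manual review will be used to identify prohibited therapies and medications that were defined in protocol Section 10.7". Table 6-6 contains three corticosteroid entries:

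- Methylprednisolone has the impact duration "From 1 st dose to 2 weeks after the last dose if route is oral". The combined betamethasone dipropionate and sodium phosphate entry carries the same oral-only condition.
- "TRIAMCINOLONE ACETONIDE" has the same 2-week impact duration with no condition on route.

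The SAP also notes: "All listed drug names in Table 6-6 were reported in NIRVANA as of finalization of this SAP". SAP 6.4.3 provides that a PSG assessment during intake of a listed drug, or in its washout ("within the timeframe specified in the impact duration column of Table 6-4" and Tables 6-5 and 6-6), "will be considered as an intercurrent event". Under SAP 4.2.2.1 such nights are dropped for the primary estimand. SAP 4.8, which lists changes from the protocol-planned analyses, does not mention corticosteroids.

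**The concern.** The list claims to apply a protocol criterion but states something else, in opposite directions for different drugs. It is narrower than the protocol for betamethasone and methylprednisolone, because systemic administration is not confined to the oral route. It is wider for triamcinolone, because a record by the inhaled route would count although the protocol permits it.

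The impact-duration column decides which Week 4 and Week 12 PSG nights enter the primary model. A night that the protocol's definition would exclude could stay in, and a night that it would retain could be removed. The same impact durations filter the baseline values of PROMIS, ISI, the sleep diary, the hot flash diary, GAD-7 and PGI-S (SAP 4.3.2.1, 4.3.2.2 and 4.4.2 to 4.4.5), so the inconsistency reaches beyond WASO.

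**Working it through.** **Passages side by side.** The core of the check is textual.

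| Record | Protocol Table 10-4 | SAP Table 6-6 as written | Result |
|---|---|---|---|
| Betamethasone or methylprednisolone, oral | Prohibited | Intercurrent event | Agree |
| Betamethasone or methylprednisolone, non-oral systemic (for example intravenous) | Prohibited | Not an event | Night kept against the protocol definition |
| Triamcinolone, systemic | Prohibited | Intercurrent event | Agree |
| Triamcinolone, inhaled | Allowed | Intercurrent event with 2-week tail | Night discarded against the protocol definition |
| Any of the three, local injection | Not classified | Not an event for the first two; an event for triamcinolone | Cannot be judged from the protocol |

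**Reach of the tail.** SAP 6.4 uses day 30 as the nominal Week 4 PSG day when the assessment is missing. With a 14-day tail, a last dose on or after about day 16 (16 + 14 = 30) touches that day.

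**The SAP writes route rules elsewhere.** Table 6-4 sets impact durations by route, and Table 6-5 exempts otic, ophthalmic and conjunctival use of moderate CYP3A inducers. An unconditioned triamcinolone row is therefore not a limit of the table's format.

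**The plan's precision figure.** Inputs from SAP Section 5: SD 33.2, 35 per arm, two-sided 90% interval, 90% probability of meeting the half-width.

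- Expected scale: t(0.95, 68) × 33.2 × √(2/35) = 13.23 minutes.
- With 90% assurance: 13.23 × √(χ²(0.90, 68)/68) = 14.65 minutes. This reproduces the stated 14.7, and the probability of a half-width of 14.7 or less is 90.7%.

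**Illustration of size.** The counts and biases here are assumed; the documents give none.

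- Wrongly losing Week 4 values in one arm, starting from 35 per arm, with the same formula:

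| Values lost | 90%-assurance half-width (min) |
|---|---|
| 0 | 14.65 |
| 1 | 14.77 |
| 2 | 14.90 |
| 3 | 15.03 |
| 4 | 15.17 |

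- If all 39 randomized per arm were evaluable, the half-width would be 13.79 minutes, so a few losses fit within the randomization allowance.
- Wrongly keeping k affected participants of 35, each biased by b minutes, shifts that arm's mean by k × b / 35. For k = 1, b = 10 this is 0.29 minutes; for k = 3, b = 30 it is 2.57 minutes.

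**The case against.** The strongest reply is that Table 6-6 is a list built from drugs already reported in the study, not a general class rule, and that the SAP version history says it was added after blinded data review. The row conditions may have been written with the recorded routes in view. If every triamcinolone record is systemic, and every non-oral betamethasone or methylprednisolone record is local, no night is misclassified. A listed drug may also have been taken only during screening washout, far from any on-treatment PSG night. The list is titled preliminary, manual review is planned, and it is to be finalized before unblinding.

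Much of this stands, and it limits what can be claimed. A reader might infer that nights have in fact been misclassified in both directions. The documents do not support that, because they give no routes, counts or timing.

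A reader might also equate each user with one lost participant, 1/78 = 1.3% of those randomized or 1/39 = 2.6% of an arm. That does not follow. Discarding is night by night, one remaining night still gives a visit value (SAP 4.1.1.1, 4.2.1), and a participant who loses Week 4 can still contribute Week 12 to the MMRM.

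Finally, a reader might treat topical or nasal triamcinolone as plainly permitted. Only inhaled use is expressly allowed; the rest depends on how the sponsor reads systemic.

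What the reply does not remove is the mismatch in the stated rule. Planned review is the right time to correct it, but review without a stated route criterion leaves the classification to case-by-case judgement. If the rows were tailored to the records, the SAP does not say so.

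**Conclusion.** The inconsistency is real and sits in the current text: two route rules for one drug class, neither matching the protocol definition that the table says it implements, and no entry in SAP 4.8. It feeds the primary estimand through SAP 6.4.3 and 4.2.2.1, and the baseline of several patient-reported measures.

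Whether any night is affected cannot be determined from the documents. The effect is probably small. On the assumed counts above, precision worsens by at most about half a minute (15.17 − 14.65 = 0.52), and an arm mean moves by about 0.3 to 2.6 minutes. The study tests no hypothesis. The first supplementary estimand uses treatment policy for this event, so no PSG night is discarded there because of it, although it answers a different question. This is a minor correction, worth making because it is cheap while the study is still blinded.

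**What to change.** Before unblinding, reconcile Table 6-6 with protocol Table 10-4:

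- Apply one explicit route criterion to all corticosteroid entries, including any added when the list is finalized.
- Have the sponsor state which routes count as systemic, and say how local injections are classified. Repeating the word systemic would leave those unresolved. Inhaled use should not count, since the protocol allows it.
- If a different rule is intended for a particular drug, record it with its reason in SAP 4.8.
- Carry the same criterion into the baseline filters that use these impact durations.

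The cost is three table cells, a short definition agreed with the clinical team, and the matching program logic. No new data are needed beyond the recorded routes.

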6.4 APPENDIX 4: Identification of Intercurrent Events

6.4.1 Premature discontinuation of study treatment

Participants who prematurely discontinue study treatment also withdrawal from study participation at the same time. No further study procedures (except for the safety follow-up visit) will be taken including PSG assessments.

Participants will likely not have a PSG assessment after discontinue study treatment. Therefore, for the identification of the ICE premature discontinuation of study treatment at week 4 and week 12, visit day 30 and day 86 will be used as the PSG assessment day respectively.

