PGI-S i						>	
PGI-C ^j		-	Starts 1	weeks after	BL		
Study medication			Starts after	er the first dos	se of study r	medication	
intake documentation						>	
Collection of						•	
handheld device							

AE = adverse event, BL = baseline, eCOA = Electronic clinical outcome assessments, EoT = End of Treatment, ePRO = Electronic patient-reported outcome, FU = follow-up, IP = In person, IRT = Interactive response technology, PK = pharmacokinetics, PSG = polysomnography, SCR = screening, SoA = Schedule of activities, T = treatment.

Questionnaires: eC-SSRS = Electronic Columbia-Suicide Severity Rating Scale, GAD-7 = Generalized Anxiety Disorder Scale -7, HFDD = Hot Flash Daily Diary, ISI = Insomnia Severity Index, PGI-C = Patient Global Impression of Change, PGI-S = Patient Global Impression of Severity, PROMIS SD SF 8b = Patient-reported Outcomes Measurement Information System Sleep Disturbance Short Form 8b, SD = Sleep Diary.

21 SEP 2023 Page: 16 of 73

- a All screening evaluations should typically be completed within 4–6 weeks with at least 14 days between SCR-1 and SCR-2 and at least 7 days at home after SCR-2 and before BL. The time required for scheduling for PSG and central reading of PSG needs to be considered for visit planning.
 b All EoT assessments (except for the safety and PK sample) are performed in the morning after the second night in the PSG lab.
- **c** If a participant discontinues prematurely from treatment, an EoT visit will be performed as soon as possible; it will comprise all assessments scheduled for the EoT visit. The EoT visit will be followed after 4 weeks by the FU visit. The handheld device will be collected at the last scheduled IP visit.
- d Eligibility check on inclusion criterion 3 (HFDD) should be assessed prior to PSG.
- e Including consultation about results obtained from screening procedures.
- f PK sample is collected on the second day in the PSG lab together with the safety lab sample.
- **g** All PSGs scheduled for T1 and T3 need to be performed under treatment, i.e., the second PSG night at EoT needs to be performed at the latest during the night after the last capsule has been taken.
- **h** The PROMIS SD SF 8b will be collected at SCR-1 and weekly from BL until EoT.
- i The PGI-S will be collected weekly from SCR-2 until EoT.
- j The PGI-C will be collected weekly following the PGI-S from 1 week after BL until EoT.

2. Introduction

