Stratification factor: The stratification factor average weekly frequency of moderate to severe HFs (including nighttime HFs) (see Section 1.2) will be assigned in the IRT system during randomization. The average weekly frequency of moderate to severe HFs is based on HFDD data and will be calculated using the 14 days prior to the visit confirmation date for HF eligibility check. A minimum of 11 days should be available for the calculation of the average weekly value. In case participants are incorrectly stratified, the actual stratification will be used in the analysis. The actual average weekly frequency of moderate to severe HFs will be the value calculated in the eDiary/electronic handheld device. If more than 10% of

Version 2.0 Page: 18 of 57

participants are incorrectly stratified, a sensitivity analysis may be performed using the assigned strata.

Study day 1: Defined as the day of start of treatment, or randomization day if participant did not take study treatment.

Study day: Study day will be calculated using study day 1 as the reference starting day. For observations on or after study day 1, the below formulae will be used:

Study day = date of observation – date of study day 1 + 1

For observations before study day 1, the formulae below will be used:

Study day = date of observation - date of study day 1

Study week: Study week will be calculated for study day >0 using the below formulae:

CEIL is a function in SAS that round up the value to the nearest integer. The calculation would follow the schedule of activities in the protocol (see Section 1.3 in protocol) where day 29 and day 85 with a plus 7-day visit window are specified for week 4 and 12 respectively. This would therefore calculate study day 1 to 7 as study week 0.

Time to event: The start date of treatment for treated participants or the randomization date for randomized participants who did not take study treatment will be used as the start date for the calculation of time to event. Therefore, the time of event will be defined as "date of event – start of treatment date (for treated participants) / randomization date (for randomized but not treated participants) +1".

Unscheduled assessments: Extra assessments (e.g., laboratory data or vital signs) associated with non-protocol visits will be included in listings, but not in the summary tables, unless otherwise specified.

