4.2 Primary Endpoint Analysis

4.2.1 **Definition of Endpoint(s)**

The primary endpoint is the change from baseline in WASO at week 4 as measured by PSG. See Section 6.2.1 for more details on the definition of WASO as measured by PSG.

PSG assessments will be performed on 2 consecutive nights during screening, at week 4 and at week 12. The baseline WASO value will be the mean value of the 2 consecutive nights at screening. Similarly, the week 4 value will be the mean value of the 2 consecutive nights at week 4. If a participant only had one PSG night for a given visit, the data from the one night will be used for the analysis.

Scheduled PSG assessments will be used but in case no scheduled assessment is available, unscheduled assessments while the participants are on treatment will be used and mapped with the following visit windows:

• if the unscheduled PSG fall within study day 22 to 45, then the assessment will be mapped to week 4. Likewise, if the unscheduled PSG fall within study day 78 to 103, then the assessment will be mapped to week 12.

If the participant discontinues treatment prematurely, the same visit windows will be used to map the EoT PSG assessment to the corresponding visit. EoT PSG assessments not mapped to week 4 or week 12 will be summarized together in the descriptive statistics but will be excluded from the model-based analysis.

When deriving study day, if the start time of the PSG recording is on or before 11:00, then the date of recording -1 will be used as the date of observation.

The change from baseline in WASO to week 4 will be calculated as below:

Change from baseline = WASO mean value at week 4 – WASO mean value at baseline

The secondary endpoint, change from baseline in WASO at week 12 as measured by PSG, will be calculated analogous to the primary endpoint.

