Although all participants are expected to be followed after ICEs temporary study treatment interruption and intake of prohibited concomitant medication, some missing data may occur. Missing values that occur while the participants continue on their randomized treatment are assumed MAR. Such missing values could be intermittent or monotone and will be imputed using a MCMC MI method.

The washout method (Wang et al. 2003) will be used to impute the unobservable data under the hypothetical scenario for the ICE premature discontinuation of study treatment. A placebo-effect is expected to be seen with the placebo group while the elinzanetant treatment effect will consist of both the placebo-effect and the effect of elinzanetant. The washout method effectively 'washes out' any pre-ICE treatment effect of elinzanetant in participants with an ICE randomized to elinzanetant, while modeling the mean placebo-effect. Missing data in participants randomized to placebo will be assumed MAR.

For participants randomized to elinzanetant, the imputation model will have the dependent variable as the endpoint measurement at week 4 with the baseline measurement and the stratification factor average weekly frequency of moderate-to-severe HFs as independent variables. The imputation model will be estimated only based on placebo participants who

Version 2.0 Page: 24 of 57

remain in the study through week 4 and have available data at week 4. Similarly, week 12 values missing after an ICE will be imputed using the same model specification but with endpoint measurement at week 12 as the dependent variable.

The imputation will be done using a regression model (PROC MI with MONOTONE REG) including covariates described above for each time point and using the MNAR statement to estimate the model from placebo participants only.

To impute missing data for participants randomized to placebo, using MAR assumptions, the imputation will be done using a regression model including measurements from all timepoints before the timepoint being imputed in addition to baseline measurement and the stratification factor (PROC MI with MONOTONE REG). All placebo participants will be included in the imputation model.

PROC MI will be run with the random seed setting SEED=22423 to produce 500 imputed datasets.

Similar analysis steps (i.e., imputation, modeling and combining results) as detailed in Section 4.2.2 will be applied.

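### SAP 6.4.1 identifies premature discontinuation against a fixed day 30 or 86 instead of the actual PSG nights, which conflicts with SAP 4.2.1, 4.2.2.1, 6.4.2 and 6.4.3 and can misclassify the event

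*SAP*

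**What the plan says.** SAP 6.4.1 reasons that women who stop treatment also leave the study and have no further procedures apart from the safety follow-up. It continues: "Participants will likely not have a PSG assessment after discontinue study treatment". For identifying the event at Week 4 and Week 12 it therefore sets that "visit day 30 and day 86 will be used as the PSG assessment day respectively". There is no condition that the PSG be missing.

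Other places treat the same women differently:

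- **Protocol Table 1-2, footnote c:** after a premature stop an EoT visit takes place as soon as possible, and "it will comprise all assessments scheduled for the EoT visit".
- **SAP 4.2.1:** "If the participant discontinues treatment prematurely, the same visit windows will be used to map the EoT PSG assessment to the corresponding visit". The windows are study days 22–45 for Week 4 and 78–103 for Week 12. The SAP version history says they were modified after blinded data review.
- **SAP 4.2.2.1:** data are discarded night by night, and only nights after the stop are lost. For how events are defined and identified, it refers to Section 6.4.
- **SAP 6.4.2 and 6.4.3:** both work from the real PSG nights. In 6.4.3 the fixed days serve as the "PSG assessment day for week 4 and week 12 respectively if PSG assessment(s) are missing"; 6.4.2 has the same limit.
- **SAP 4.2.3.1 (first supplementary analysis):** "Missing values that occur while the participants continue on their randomized treatment are assumed MAR". Elinzanetant values unobservable because of premature discontinuation are imputed from placebo participants by the washout method.

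**The concern.** Day 30 is only the earliest possible second night of the Week 4 visit. A woman who stops after day 30 but before a later, in-window PSG has discontinued before her assessment, yet the day-30 test says she has not. In the other direction, a woman whose EoT PSG was recorded on drug shortly before day 30 is counted as having the event at that visit, although neither night followed the stop.

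The status feeds three things: the intercurrent-event table and the boxplots split by event status (SAP 4.1.3); the discard of post-discontinuation data; and the choice between MAR and washout imputation in the first supplementary analysis. The tipping-point analysis was removed (SAP 4.8), so that washout analysis is the only planned departure from MAR. For one woman, 6.4.1 and 4.2.2.1 can give opposite answers, and the SAP does not say which governs.

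**Working it through.** **The fixed days.** SAP 4.1.2 describes the schedule as one "where day 29 and day 85 with a plus 7-day visit window are specified for week 4 and 12 respectively". SAP 4.2.1 adds: "PSG assessments will be performed on 2 consecutive nights during screening, at week 4 and at week 12". If the first night is the visit day, the nominal second nights are 29 + 1 = 30 and 85 + 1 = 86, which reproduces the SAP's figures. With the +7 window the first night p runs over days 29–36 and the second over days 30–37 (Week 12: 85–92 and 86–93).

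**Conventions.** Let s be the day of last dose. A night is off drug if its day is later than s. The fixed-day test flags a stop before day 30. The text leaves a stop on day 30 itself open, so only s > 30 is counted as missed. The woman is fully adherent until she stops.

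**Missed stops, Week 4.** For each pair (p, p + 1), a stop is missed when 31 ≤ s ≤ p. Does 6.4.2 catch it as a temporary interruption?

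- Days with intake among the last seven (p − 5 to p + 1) number s − p + 6. This is below 5 only when s ≤ p − 2.
- The lowest compliance is 31/37 = 83.8%, so the 80% criterion never applies.

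| Nights | Missed last-dose days | Labelled interruption by 6.4.2 | Caught by neither rule |
|---|---|---|---|
| 29–30, 30–31 | none | 0 | 0 |
| 31–32 | 31 | 0 | 1 |
| 32–33 | 31–32 | 0 | 2 |
| 33–34 | 31–33 | 1 | 2 |
| 34–35 | 31–34 | 2 | 2 |
| 35–36 | 31–35 | 3 | 2 |
| 36–37 | 31–36 | 4 | 2 |
| Total | 21 | 10 | 11 |

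Week 12 gives the same counts for last-dose days 87–92. These are possible date patterns, not expected numbers of women. If the mapping window to day 45 is used in place of the visit window, missed stops could run to day 44.

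**Example of the 11.** Last dose day 32, EoT PSG on nights 33 and 34, mapped to Week 4. The day-30 test finds no discontinuation. Under 6.4.2, intake on days 28–32 is 5 of 7 days, and capsules are 64/68 = 94%, so there is no interruption either. Yet both nights follow the stop.

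**Example without a PSG.** Appointment day 35, last dose day 31, no recording. Section 6.4.1 tests at day 30, and 6.4.2 also falls back to day 30, when she was still adherent. Neither rule records an event at Week 4.

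**On-drug EoT PSGs.** With nights s − 1 and s both on drug and inside the mapping window, s − 1 ≥ 22 and s < 30 give s = 23 to 29. For Week 12, s = 79 to 85. On each of these 7 last-dose days per visit the woman is counted as having the event at the visit.

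**Where each misclassification leads.**

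- *Primary MMRM:* by actual night, 4.2.2.1 discards the off-drug nights and keeps the on-drug ones. The 10 patterns labelled as interruption are discarded in any case. A missing value is MAR whether or not it is flagged.
- *First supplementary analysis:* under the 6.4.1 status, the 10 patterns would keep their off-drug data under treatment policy and the 11 would keep them with no event recorded, although Table 4-3 discards data after discontinuation. The missing elinzanetant value in the no-PSG example could go to MAR instead of washout.

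**The case against.** The strongest reply is that 4.2.2.1 already states the right rule for the data: it acts on individual nights and discards only those after the stop. Table 1-2 of the SAP likewise discards only what follows the event. A reader might infer from 6.4.1 that the primary data set is biased in both directions; the documents do not support that. The claim would need 6.4.1 to override 4.2.2.1, and the only basis is the cross-reference to 6.4 for how events are identified. What remains is a conflict of wording to reconcile.

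A reader might also infer that on-drug EoT recordings are thrown away. They are not: only data after the event are discarded, and washout imputes only unobservable values. Counting a woman whose last dose was on day 25 as a discontinuer before nominal Week 4 is itself defensible. The fault is that the table would mark a visit whose two nights were both on drug.

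Further points stand. SAP 4.2.3.1 ties MAR to women who continue on treatment, so a woman who stopped on day 31 need not be routed there; the text just does not settle it. Only the elinzanetant arm is exposed to that routing, because missing placebo values are MAR regardless. Protocol footnote g wants PSGs under treatment, Section 7.1 lets medically inappropriate EoT procedures be omitted, and Section 7.2 asks for the EoT visit only if possible, so off-drug PSGs should be rare. Events are also reviewed before unblinding (SAP 4.1.3).

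None of this explains why 6.4.1 alone lacks the condition found in 6.4.2 and 6.4.3, or why its premise differs from 4.2.1.

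**Conclusion.** Wrong as written, minor. The rule in 6.4.1 does not identify stops on days 31–36 (87–92) before an in-window PSG night. Of the 21 Week 4 patterns, 10 become temporary interruptions and 11 are caught by neither rule. It also attaches the event to on-drug EoT PSGs with last dose on days 23–29 (79–85).

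Provided 4.2.2.1 is applied by actual night, the primary MMRM is largely unaffected. The effect is on the event counts, the boxplots and possibly the discard and the washout-versus-MAR routing in the first supplementary analysis.

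The number of women is probably small; the documents give no count. For scale, one woman is 1/39 = 2.6% of a planned arm. If her retained or imputed Week 4 change differed from the appropriate one by 20 to 40 minutes (an assumption, not a figure from the documents), the arm mean in the supplementary analysis would move by about 20/39 = 0.5 to 40/39 = 1.0 minute. The planned half width is 14.7 minutes, and no hypothesis is tested.

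The counts assume that the first PSG night is the visit day, that the stop day is the last-dose day, and that the woman was adherent until then.

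**What to change.** Before unblinding, amend the SAP as follows:

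- **6.4.1, rule:** a PSG night counts as after premature discontinuation if it is later than the date of last dose. Use day 30 or 86 only if no PSG is available for the visit, as in 6.4.3. Say how a last dose on day 30 or 86 itself is classified.
- **6.4.1, premise:** replace the statement that no PSG is taken after discontinuation, so that it agrees with 4.2.1.
- **One flag:** derive the intercurrent-event table, the 4.2.2.1 discard and the 4.2.3.1 washout route from this single status.
- **4.2.3.1:** state that a missing elinzanetant value is MAR only if the woman had not permanently stopped treatment before the PSG was due. This is needed because the day-30 fallback alone still leaves the day-31 stop without a PSG unflagged.

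Moving the fallback to the end of the visit window (day 37 or 93) is not recommended. It would disagree with the day 30/86 fallback in 6.4.2 and 6.4.3, and would label as a discontinuation a PSG missed on drug on days 29–30 if the woman stopped by day 37.

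The cost is a few lines of SAP text and one date comparison in the programming. No new data are needed.
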